**Study Protocol and Statistical Analysis Plan**

**Trial registration number: NTC02729545**

**Document Date: 28/3/2018**

# Study Protocol and Statistical Analysis Plan

## Study design

The study was a randomized, drug-controlled, parallel group trial to determine the efficacy and safety of Tung's acupuncture for sex hormones compared with the oral contraceptive (CPA/EE) in patients with PCOS. The trial was performed at the Acupuncture and Gynecology Department of Beijing Hospital of Integrated Traditional Chinese and Western Medicine. Participants were recruited through advertisements on local newspapers and posters and signed informed consent before study participation. The study lasted 28 weeks: a 1-4-weeks baseline period, 12-week treatment period, and a 12-week follow-up period.

## Participants

PCOS was diagnosed according to the Rotterdam criteria: ultrasound-verified polycystic ovaries ( $\geq 12$  follicles of 2–9 mm and/or ovarian volume  $\geq 10$  ml in one or both ovaries), oligo/amenorrhea, or clinical signs of hyperandrogenism (hirsutism or acne). Participants were considered eligible upon meeting the following conditions: 1) 18–45 years old; 2) met the diagnostic criteria for polycystic ovary syndrome, and no reproductive requirement in the six months; 3) volunteered to join this research and give informed consent prior to receiving treatment.

The exclusion criteria included: 1) hypertensive patients with blood pressure exceed 160/100 mmHg; 2) patients with a history of thrombosis, cerebrovascular disease, cancer, liver disease or liver dysfunction, hyperlipidemia, mental disorder and severe infection; 3) had taken any pharmacological treatments affecting reproductive endocrine system, or received acupuncture in the previous 3 months; 4) smoked more than 15 cigarettes a day; 5) patients with pacemakers, metal allergies or severe fear of acupuncture.

## Randomization and blinding

Eligible participants were randomly allocated into either acupuncture group or CPA/EE group in a ratio of 1:1 by a computer-generated, randomly location sequence (random list generated with SPSS 13.0). The random number and group assigned were sealed in the envelope. Randomization was performed by an independent administrator who had no other role in this study. All other individuals involved in the study including patients, practitioners, and outcome assessors were blinded to the randomization procedure. In this study, physicians could not be blinded due to the nature of the intervention. The acupuncturists had to know the group assignment because of manipulation. Data collection was performed by 2 blinded evaluators. Data entry and analysis was undertaken blind to the study group. Apart from the differences in treatment methods between the two groups, all subjects were treated as equally as possible.

## Treatment protocol

Acupuncture group: the acupuncture group received acupuncture treatments twice per week for 12 weeks with a total of 24 times. Huatuo brand needles (size 0.20mm×25mm, 0.20mm×40mm, manufactured by Suzhou Medical Appliance, Suzhou, Jiangsu Province, China) together with SDZ-V Electro-Acu Stimulators (Suzhou Medical Appliance, Suzhou, Jiangsu

Province, China) were used. The study took Tung's acupoints as main acupuncture points, which were Fuke, Huanchao, Tianhuang, Renhuang, as well as the traditional acupoints Guanyuan (CV4) and Zigong (EX-CA1). The location of these acupuncture points referred to *Tung's Acupuncture*. Fuke point (Fig 1) is on the ulnar side of the proximal joint of thumb. There are two points up and down, 1/3 of the distance away from the interphalangeal joint. Huanchao point is on the middle of the central joint, on the ulnar side of ring finger. Tianhuang point is at the same location of Yin Lingquan (SP9), on the medial side of the shank, on the lower border of the medial condyle of the tibia. Renhuang point is at the same location of San Yinjiao (SP6), on the medial side of the shank, 3 cun directly above the tip of the medial malleolous, on the posterior border of the medial aspect of the tibia. The specific manipulation was as follows: Fuke were inserted vertically closed to the bone (depth,7.5mm) with 0.20 mm×25mm needles, Huanchao was inserted vertically closed to the bone (depth,5-7.5mm) with 0.20 mm×25mm needle, the bilateral two points alternately used (left Fuke with right Huanchao, right Fuke with left Huanchao). Bilateral Tianhuangs, Renhuangs were inserted vertically with a depth of 20-30mm, and stimulated manually by rotating the needle to evoke de qi (defined as numbness, heaviness, pressure, soreness, or tingling). The insertion of CV4 and EX-CA1 was straight to the abdominal muscle until the needle sensation was achieved. Bilateral EX-CA1s were connected to an electrical stimulator with a continuous wave of 20Hz, and slowly increased the current intensity to a slight tremor in the abdomen. At the same time a moxa box was administered via smokeless moxa stick on the lower abdomen for 30minutes.

CPA/EE group: CPA/EE (Diane-35, Bayer Healthcare Co. Ltd) was taken orally from the 8th day of menstrual cycle or any day for patients with amenorrhea, one tablet per day, and the pill was administered for 21 days consecutively. The patients then stopped taking the pill for seven days and on the eighth day, the patients began the pill again for three menstrual cycles (28 day cycles). Patients were asked to visit the doctor every menstrual cycle, in order to receive the medicine of next cycle and communicate with the doctor about their physical condition, or the patients were required to visit the doctors if they feel any discomfort.

## Outcome measurements

The change in LH/FSH ratio from baseline at end of treatment was considered as the primary outcome in this study, and secondary outcomes include the changes in BMI, FSH, LH, TT, ovarian volume, polycystic ovary number and menstrual frequency at week 12 and 24 from baseline. The blood samples were measured at the 2-3rd Day of menstrual cycle during the baseline period, after the last treatment and 12-week follow-up period. If no ovulation or bleeding had occurred during the period, the measurements were taken one week after the end of treatment and 12-week follow-up period. The sex hormones were analyzed by chemiluminescent microparticle immunoassay at the medical laboratory of Beijing Hospital of Integrated Traditional Chinese and Western Medicine.

The polycystic ovary number and volume were measured by ultrasound, which were together with BMI and menstrual frequency taken 3-7th days after menstruation during the baseline period, after the last treatment and 12-week follow-up period. The polycystic ovary number was defined as the number of ovaries with cysts/follicles (>12 cysts), the ovarian volume was measured in three dimensions by an experienced sonographer who was blinded to the group.

Safety evaluation included acupuncture related adversary events such as hematoma, fainting, severe pain, post-treatment soreness and local infection during and after acupuncture, as well as

CPA/EE related adversary events like vomiting, nausea, headache and skin reactions during taking pills.

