### Sample size

This trial was a difference test design, the primary outcome measure was the change of the ratio of LH/FSH from baseline at the end of treatment. Based on the results of our pilot study and previous studies, we anticipated a mean difference in the ratio of LH/FSH was 1.2 (SD, 0.8) in CPA/EE group, and 1.68 (SD, 0.2) in Tung's acupuncture group. Sample size was determined with a 0.05-probability of a type I error and 80% power, 2 sided test with a 20% attrition rate. 30 patients will be needed for each group, which implied a total sample size of 60 participants for the entire trial.

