### Statistical analysis

Statistical analysis performed using SPSS 13.0 statistics software (SPSS Inc, Chicago, IL, USA) and the statistician was blinded from group allocation. The Kolmogorov-Smirnov test was used to test the normal distribution of continuous variables. Continuous variables were presented by mean (standard deviation) if they were normally distributed or by median with interquartile range if they are not normally distributed. The modified intention-to-treat (ITT) approach was used to analyze the study group, all subjects with at least having one treatment data in randomized groups were included. A paired samples t test or Wilcoxon Matched-Pairs SignedRanks test was examined to compare the differences between the quantitative indices before and after treatment in one group, while an independent sample t test or Mann-Whiney U test was used for comparison between groups. The entire statistical test used bilateral examination and estimation of the median with 95% CI was calculated.

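### The only follicle-based secondary outcome is a 0–2 count of ovaries above a cut-off, which loses power to detect a difference in follicle number

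*Combined protocol and SAP*

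**What the plan says.** The Outcome measurements section lists the secondary endpoints: "secondary outcomes include the changes in BMI, FSH, LH, TT, ovarian volume, polycystic ovary number and menstrual frequency at week 12 and 24 from baseline". It defines the follicle endpoint as follows: "The polycystic ovary number was defined as the number of ovaries with cysts/follicles (>12 cysts". With two ovaries, the score is 0, 1 or 2 and its change lies between −2 and +2. On how it is obtained, the section says only: "The polycystic ovary number and volume were measured by ultrasound". Neither that section nor Statistical analysis mentions a follicle count per ovary.

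The Participants section sets the ultrasound entry criterion in terms of "follicles of 2–9 mm and/or ovarian volume", with thresholds of at least 12 follicles and at least 10 ml. It also lists oligo/amenorrhea and clinical hyperandrogenism as diagnostic features.

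The Statistical analysis section has one between-group rule for quantitative measures: "an independent sample t test or Mann-Whiney U test was used for comparison between groups". It does not name the polycystic ovary number or say how a heavily tied three-level score is to be handled.

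**The concern.** Cutting each ovary's follicle number at a threshold and adding two yes/no results removes most of the information about how far the number moved. The score responds only to crossings of the cut-off. It therefore depends on how close a woman's ovaries were to 12 at baseline as well as on the size of the fall.

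This comes from the three-level range, not from where the line is drawn. The outcome uses more than 12 and the entry criterion uses 12 or more, so an ovary with exactly 12 follicles meets the entry criterion but scores 0. Aligning the two would leave the insensitivity in place.

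What is at stake is one secondary endpoint in a small trial. A null result on the score could mean no effect on follicle number, or an effect the scale did not register. A positive result could come from changes of one or two follicles near the cut-off.

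**Working it through.** **1. Evaluable number per arm.** Inputs from the Sample size section: "we anticipated a mean difference in the ratio of LH/FSH was 1.2 (SD, 0.8) in CPA/EE group", "1.68 (SD, 0.2) in Tung's acupuncture group", and "0.05-probability of a type I error and 80% power, 2 sided test with a 20% attrition rate".

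- Difference: 1.68 − 1.2 = 0.48.
- Average variance: (0.8² + 0.2²)/2 = (0.64 + 0.04)/2 = 0.34, so SD = 0.583.
- n per arm = 2 × 0.34 × (1.960 + 0.842)² / 0.48² = 0.68 × 7.849 / 0.2304 = 23.2, rounded up to 24.
- With 20% attrition: 24 / 0.80 = 30 per arm, 60 in total.

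The stated sample size reproduces. It was set for the LH/FSH ratio. The documents give no power for the follicle score, and 24 per arm is used below.

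**2. What the definition does.** This needs no assumptions.

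| Both ovaries go from | Fall in follicles | Score | Change in score |
|---|---|---|---|
| 30 to 13 | 17/30 = 57% | 2 to 2 | 0 |
| 13 to 12 | 1/13 = 8% | 2 to 0 | −2, the maximum |
| 12 or fewer, any fall | any | 0 to 0 | 0 |

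The last row can occur in this trial, because a woman can enter on ovarian volume or on the other diagnostic features. The documents do not say how many such women to expect.

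**3. Effect on power.** The documents give no mean, SD or treatment effect for follicle number, so every input except the 24 per arm is assumed:

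- baseline mean 14, 18 or 22 follicles per ovary, SD 6;
- correlation of 0.8 between a woman's two ovaries;
- counting SD 2 or 4;
- mean fall of 10% in one arm and 30% in the other;
- between-woman SD of the fall 0, 20 or 30 percentage points.

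That makes 3 × 2 × 3 = 18 settings. In each simulated trial, counts were rounded, the more-than-12 rule was applied to each ovary, and Mann-Whitney (two-sided 0.05) was applied to the change in the score and to the change in mean count.

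| Setting | 0–2 score (means 14, 18, 22) | Mean count (means 14, 18, 22) |
|---|---|---|
| Counting SD 2, same percentage fall for all women in an arm | 63%, 71%, 59% | 97% or higher in all three |
| Counting SD 2, SD of fall 20 points | 38%, 48%, 46% | 69%, 78%, 81% |
| Counting SD 2, SD of fall 30 points | 25–33% | 45–54% |
| All 18 settings, including counting SD 4 | about 20–72% | about 31–100% |

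The count had higher power in all 18 settings.

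**4. A differently built model.** Here the falls are absolute: 2 follicles per ovary in one arm and an extra 3 or 4 in the other. Baseline mean is 12–26, patient SD 5, ovary/visit SD 3, with 24 per arm. The t test is used for the count and Mann-Whitney for the score.

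| Extra fall | 0–2 score | Mean count |
|---|---|---|
| 3 per ovary | 13–46% | 88–93% |
| 4 per ovary | 25–68% | 98–99% |

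Among women in the arm with the larger fall whose mean count fell by 4 or more per ovary, about 33–86% had an unchanged score, depending on the baseline mean.

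**The case against.** The case on the other side has five parts.

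- **Full counts may not exist.** A reader might infer that the sonographer already has complete counts and the plan throws them away. The documents do not support this. Classifying an ovary as above 12 needs counting only to 13, and the sentence that mentions a blinded sonographer attaches to ovarian volume. This stands. The plan's text is in the past tense, so the counts may not be recoverable.
- **The score is not bound to fail.** A reader might infer that it will probably miss a real difference. In the most favourable settings its power is 59–71%, so it would detect the assumed difference more often than not. In the less favourable settings it falls to about 20%, but there the count also falls, to as little as 31%. What can be defended is a loss of power relative to the count.
- **The ovary is measured in another way.** A reader might infer that a null score says little about the ovary. Ovarian volume is a separate continuous secondary outcome, so the limitation applies to follicle number only.
- **The test is not invalid.** Mann-Whitney can be used on ordinal data with ties, and the Statistical analysis section never says this score is to be treated as continuous. The problem is lost efficiency, not bias.
- **The number of polycystic ovaries is a legitimate, readable measure** related to the entry morphology, so preferring a count is partly a choice of what to estimate. This is fair, and it is a reason to keep the score as a description. It does not make the score a sensitive measure of follicle number.

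**Conclusion.** The point holds as a low-cost improvement to one secondary outcome. That the score ignores large falls above the cut-off, rewards one-follicle falls across it and cannot improve from 0 follows from the definition alone.

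The size of the power loss rests on assumed follicle distributions and effects. Over the 18 settings it is about 20–72% for the score against 31–100% for the mean count. The direction was the same in every setting, including the differently built model. Count power of 97% or higher belongs to the favourable end, where every woman in an arm has the same percentage fall and counting error is small. It should not be quoted alone.

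The LH/FSH primary outcome and the total of 60 are not affected.

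**What to change.** At the ultrasounds already scheduled (baseline, after the last treatment, after the 12-week follow-up), record the full number of 2–9 mm follicles in each ovary, the size range used in the Participants section. Define the follicle outcome as the change from baseline in mean follicles per ovary (average of left and right) at weeks 12 and 24. It can be compared between groups with the tests already named. Keep the number of polycystic ovaries as a descriptive shift table by arm.

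The cost is a little extra scanning time to count beyond 12. No extra patients, visits or equipment are needed. Where only the above/below classification was recorded, report the 0–2 score and state that it is insensitive to changes in follicle number.

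### Adverse events are defined and timed separately for each arm, so totals by arm cannot support the comparative safety statement the trial sets out to make

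*Combined protocol and SAP*

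**What the plan says.** The Study design section describes a "drug-controlled, parallel group trial to determine the efficacy and safety of" the acupuncture regimen under study, and it words the comparison as "for sex hormones compared with the oral contraceptive (CPA/EE) in patients with PCOS". Safety relative to the comparator is therefore part of the aim. The same section gives a "12-week treatment period, and a 12-week follow-up period".

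Safety collection is described once, at the end of Outcome measurements. For acupuncture: "Safety evaluation included acupuncture related adversary events such as hematoma, fainting, severe pain, post-treatment soreness and local infection during and after acupuncture". For the comparator, it covers CPA/EE "related adversary events like vomiting, nausea, headache and skin reactions during taking pills". That section sets time points for hormones, ultrasound, BMI and menstrual frequency, but none for harms. The Statistical analysis section gives no method for adverse events.

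Three other statements bear on the point:

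- **Contact, acupuncture (Treatment protocol):** "the acupuncture group received acupuncture treatments twice per week for 12 weeks with a total of 24 times".
- **Contact, CPA/EE (Treatment protocol):** a visit each cycle to collect the next supply and discuss physical condition, plus a visit whenever discomfort is felt.
- **Data collection (Randomization and blinding):** "Data collection was performed by 2 blinded evaluators", and, apart from the treatments themselves, "all subjects were treated as equally as possible".

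**The concern.** Comparing harms between arms requires the same kind of event, counted over the same period and asked about in the same way. Here each arm has its own attribution (related to acupuncture, or related to CPA/EE), its own examples and its own window. Nothing says whether a headache in an acupuncture patient, or a fainting episode in a CPA/EE patient, would be recorded.

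If the totals were set against the aim in Study design, a difference could come from what was eligible to be counted, for how long, or how often patients met staff, rather than from the treatments. Equal totals would be no easier to interpret. Adding patients would not help, because the problem is comparability and not precision.

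**Working it through.** The plan states no safety figure, so there is none to reproduce. The check sets the two descriptions side by side and then uses the plan's own schedule.

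**1. Definitions.**

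| | Acupuncture | CPA/EE |
|---|---|---|
| Attribution | Related to acupuncture | Related to CPA/EE |
| Examples | Hematoma, fainting, severe pain, soreness, local infection | Vomiting, nausea, headache, skin reactions |
| Window | During and following acupuncture, no stated end | While tablets are taken |
| Time of asking | Not stated | Not stated |

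The lists share no event. They are worded as examples, so other events are not excluded, but the attribution still ties recording to the assigned treatment.

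**2. Windows.** Inputs are the 12-week treatment and 12-week follow-up periods (Study design), and two sessions a week and three 28-day cycles with 21 tablet days each (Treatment protocol).

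- Acupuncture, around each session: 2 × 12 = 24 session days.
- Acupuncture, over the course: 12 × 7 = 84 days.
- Acupuncture, through follow-up: 24 × 7 = 168 days.
- CPA/EE, tablet days: 3 × 21 = 63.
- CPA/EE, first to last tablet: 21 + 7 + 21 + 7 + 21 = 77 days.
- CPA/EE, three full cycles: 3 × 28 = 84 days.

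Ratios of acupuncture to CPA/EE:

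- Session reading: 24/84 = 0.29 to 24/63 = 0.38.
- Course reading: 84/84 = 1.00 to 84/63 = 1.33.
- Follow-up reading: 168/84 = 2.00 to 168/63 = 2.67.

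The acupuncture window may thus be shorter than, equal to or longer than the other. The follow-up period is 168 − 84 = 84 days, half of the time after treatment starts. It lies outside the CPA/EE window on all three readings, and inside the acupuncture window on only one.

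**3. Contact.** Acupuncture has 24 sessions. CPA/EE has about 3 scheduled visits (2 to 4, depending on whether the first supply and a last visit count). Adding the two assessments that both arms share, after treatment and after follow-up, gives 24 + 2 = 26 against about 3 + 2 = 5 (4 to 6), before any discomfort visits. These are opportunities to report. The plan does not say at which of them adverse events were recorded.

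**4. Direction.** More contact could raise acupuncture counts. The instruction to attend for discomfort, stated only for CPA/EE, could raise counts there. Treatment-specific attribution could lose events in either arm. The documents give no basis for netting these out.

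**5. Precision of a common comparison.** I take 30 per arm from Sample size and assume that 10% to 30% of patients have an event, equally in both arms. With Wilson limits l and u for each arm's proportion p, the Newcombe 95% half-width at equal counts is √[(p − l)² + (u − p)²].

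- 3/30 against 3/30: l = 0.035, u = 0.256, half-width √(0.065² + 0.156²) = 0.169.
- 6/30 against 6/30: l = 0.095, u = 0.373, half-width 0.202.
- 9/30 against 9/30: l = 0.167, u = 0.479, half-width 0.223.

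That is about 17 to 22 percentage points.

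**The case against.** The best defence is that nothing stated is miscalculated. No between-arm test of adverse events is planned, safety is neither the primary nor a listed secondary outcome, and no passage claims that one treatment is safer. Harms of needling and of tablets differ by nature, so separate lists are reasonable. Both arms had visits, blinded evaluators collected data, and equal treatment was intended. The text is almost wholly in the past tense, so a new collection rule may come too late.

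Much of this stands, and it keeps the point minor. It does not remove it, because safety against CPA/EE is a stated aim and the only collection rule cannot serve it. The sentences on blinded evaluators and equal treatment do not mention adverse events or supply a common rule, and applying the safety text by arm requires knowing the arm. Treatment-specific lists are sound for description, but a comparison needs a common layer beside them.

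A reader might go further and infer that acupuncture was watched longer and about eight times as often (24 against 3), so that its harms would be overcounted. The documents do not support that. The needling examples are largely tied to a session, so the window may mean the time around each session, which is shorter than the CPA/EE window. Contacts are also not enquiries.

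**Conclusion.** The point holds as a limit on interpretation. As written, totals by arm cannot support a statement that either treatment is safer, because definition and window differ by arm and no common time of asking is set.

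The size of any bias cannot be given. The window ratio runs from 0.29 to 2.67 according to how two phrases are read, and the contact figures do not measure ascertainment. The direction is equally open, so a claim that the plan favours one arm would go beyond the text. So would a claim that other events were barred from recording, since the lists are only examples.

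Descriptions of harms within each arm, the primary outcome and the sample size are untouched. The conclusion assumes that no separate collection rule exists outside this document. Severity: minor.

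**What to change.** **If collection can still be changed.** In both arms, record all adverse events regardless of presumed cause, over one window from first treatment to week 24. Use one identical form containing both current lists plus an open question. The patient completes it, or treating staff take it, once per 28-day cycle at existing visits and again at the week-24 assessment: about four time points. Keep the forms from the blinded outcome evaluators, since answers about needling or tablets would often reveal the arm. Report the proportion of patients with at least one event per arm, with a risk difference and 95% CI as estimation only. Report treatment-specific events separately.

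**Cost.** Wording in the case report form and analysis plan, and a few minutes per visit. More minor events will be recorded, and events in weeks 13 to 24 will rely on recall. The comparison will remain imprecise, as the half-widths above show.

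**If collection is complete.** Report events descriptively by arm, state that definitions, windows and contact differed, and make no comparative safety claim. The cost is reporting wording only.

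### The plan promises safety compared with CPA/EE but specifies no objective safety measurement after entry, no event item common to both arms and no safety analysis

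*Combined protocol and SAP*

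**What the plan says.** The Study design section states the aim as "to determine the efficacy and safety of Tung's acupuncture for sex hormones compared with the oral contraceptive (CPA/EE) in patients with PCOS". Comparative safety is therefore a declared objective.

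The Participants section excludes "hypertensive patients with blood pressure exceed 160/100 mmHg" and "patients with a history of thrombosis, cerebrovascular disease, cancer, liver disease or liver dysfunction, hyperlipidemia, mental disorder and severe infection". These criteria apply to both arms.

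The Outcome measurements section schedules hormones, ultrasound, BMI and menstrual frequency at baseline, after the last treatment and after follow-up. Its safety text has two parts. For acupuncture: "Safety evaluation included acupuncture related adversary events such as hematoma, fainting, severe pain, post-treatment soreness and local infection during and after acupuncture". For the drug: "CPA/EE related adversary events like vomiting, nausea, headache and skin reactions during taking pills".

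In the Treatment protocol section, CPA/EE patients attend each cycle "in order to receive the medicine of next cycle and communicate with the doctor about their physical condition", and in addition "the patients were required to visit the doctors if they feel any discomfort". No measurement is named for these visits.

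The Statistical analysis section describes within-group and between-group tests for quantitative variables. It does not mention adverse events or any other safety data.

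**The concern.** The plan regards blood pressure, liver function and lipids as important enough to decide who may enter, but does not say that any of them is looked at again. Its safety evaluation names clinical events only. An event list, however open, captures what someone notices or asks about. A change in blood pressure, a liver enzyme or a lipid value generally needs a reading or an assay to be seen (a general premise, not a statement in the documents).

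The two lists also do not meet. One arm is described by needle effects and the other by pill symptoms, so no named item can be set against itself across arms. With no safety analysis specified, a reader of the eventual report could not tell how a comparative statement was reached. The statement at risk is one that acupuncture is safe, or safer than CPA/EE, drawn from data that say nothing about the measurable conditions in the trial's own exclusion list.

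**Working it through.** **Step 1. Entry criteria against post-entry assessment**, from Participants, Treatment protocol and Outcome measurements.

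| Condition | Entry criterion | Numeric limit | Post-entry assessment specified |
|---|---|---|---|
| Blood pressure | yes | 160/100 mmHg | none |
| Liver disease or dysfunction | yes, by history | none | none |
| Hyperlipidemia | yes, by history | none | none |
| Thrombosis, cerebrovascular disease | yes, by history | none | not named; could be recorded under the open lists |

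Sex hormones are the only blood assays named. BMI is measured in both arms but is listed as a secondary outcome, not a safety measure.

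**Step 2. Overlap of the event lists.** Acupuncture: hematoma, fainting, severe pain, soreness, local infection. CPA/EE: vomiting, nausea, headache, skin reactions. Items in common: 0.

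**Step 3. Patients and exposure.** The Sample size section gives 30 per group and 20% attrition, so 30 × (1 − 0.20) = 24 complete. Three 28-day cycles are 84 days.
- 30 × 84 / 365.25 = 6.9 person-years on CPA/EE cycles.
- 24 × 84 / 365.25 = 5.5 person-years if only completers count.

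**Step 4. What a zero count can exclude.** With 0 events in n patients, the one-sided 95% upper bound is 1 − 0.05^(1/n).
- n = 30: 1 − 0.05^(1/30) = 9.5%.
- n = 24: 1 − 0.05^(1/24) = 11.7%.

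**Step 5. Chance of seeing at least one event**, 1 − (1 − p)^n. The documents give no event rates, so p is an assumed range.

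| Assumed true risk p | n = 30 | n = 24 |
|---|---|---|
| 0.1% | 3% | 2% |
| 1% | 26% | 21% |
| 5% | 79% | 71% |

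**Step 6. Common events.** For 0/30 against 6/30, the one-tail Fisher probability is C(30,6)/C(60,6) = 593,775 / 50,063,860 = 0.0119. Doubling for the symmetric tail gives a two-sided p of about 0.024. A difference of this size in a common event could be detected if the event were recorded in the same way in both arms.

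**The case against.** The strongest reply is that the document is short and its lists are open. *Such as* and *like* introduce examples, so a thrombosis or stroke that came to attention could be recorded. Staff can see hematoma, fainting, infection and skin reactions, and a doctor sees CPA/EE patients every cycle. The Participants section also gives the exclusions for both arms without calling them risks of CPA/EE. Much of the text is in the past tense, so adding measurements may no longer be possible. All of this stands. It limits the point to what is not specified; it does not supply a measurement, a common item or an analysis.

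A reader might infer several stronger things that the documents do not support:

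- **That safety rests only on symptoms patients notice themselves, or that harms would go unrecorded.** The open lists and doctor visits contradict this. Silence in the plan does not prove that nothing was measured.
- **That entry limits should have been applied again at each supply visit.** The Participants and Treatment protocol sections do not contradict each other here. Only blood pressure has a numeric limit, so a count of patients newly crossing a liver or lipid limit cannot be defined from the plan. Clinical limits and actions are for the sponsor's clinicians.
- **That only continuous markers could separate the arms.** The 0/30 against 6/30 example shows otherwise for common events, and the documents give no SD or effect size for any marker.
- **That assays on the existing samples would show changes during treatment cycles.** The post-treatment sample is drawn after the last treatment, so it would show change by the end of treatment only.

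**Conclusion.** The point holds as a gap between a stated objective and the data planned to meet it. Specified post-entry measurements of blood pressure, liver function and lipids: 0. Named event items common to both arms: 0. Safety analyses described: 0. The plan as written cannot support a comparative safety conclusion on those three measures, and at 30 per arm a zero count cannot exclude a true risk below 9.5% (11.7% with 24).

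This should be corrected, but it does not touch the primary LH/FSH comparison. The finding that nothing is specified rests on reading the whole document and assumes that no separate safety or laboratory manual fills the gap. The two bounds assume that every event is ascertained; incomplete ascertainment would make a zero count less informative still.

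**What to change.** 1. In Outcome measurements, add blood pressure as a safety outcome in both arms at contacts that already exist: baseline, the end-of-treatment and follow-up assessments, and the CPA/EE cycle visits, each with a matching acupuncture session.
2. If the existing samples are suitable, which the documents do not state, add change in liver enzymes and lipids at baseline, end of treatment and follow-up. Say that these show change by the end of treatment and not within cycles.
3. Record all adverse events in both arms on one common list that names thrombotic and cerebrovascular events.
4. In Statistical analysis, add a safety paragraph: events reported by arm, and the continuous measures compared with the between-group tests already named there.
5. State that freedom from rare events cannot be concluded from 30 per arm, and give the one-sided 95% upper bound with any zero count.
6. If measurement is no longer possible, state what was assessed and limit the safety conclusion to the events collected.

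The cost is cuff readings at existing contacts, optional routine assays, one safety table and a sentence limiting the conclusion. The fallback in item 6 needs text only.
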